## 6.2.2 Baseline Assessments

The following assessments will be performed at baseline after randomization (i.e., at study inclusion, not necessarily at ICU or intermediate care unit admission date):

- Vital signs (temperature, heart rate, respiratory rate, oxygen saturation, and blood pressure)
- Physical examination
- 12-lead electrocardiogram (ECG)
- Acute Physiology And Chronic Health Evaluation II (APACHE II) score
- Simplified Acute Physiology Score 2 (SAPS-2) score
- Sequential Organ Failure Assessment (SOFA) score
- Quality of life questionnaire (EQ-5D)
- Urine collection during  $6 \pm 1$  hour period with registration of exact time of collection and determination of urine volume (only required when possible within the 24-hour time window from first AKI diagnosis to treatment)
- Local laboratory assessments
  - Hematology
  - Clinical chemistry, excluding AP activity
  - Note: Platelets, bilirubin, creatinine, and urine output are required to obtain a SOFA score.
- Central laboratory
  - Tubular injury biomarkers (e.g., KIM-1, IL-18, GST-alpha) in urine
  - Biomarkers for systemic inflammation (e.g., IL-6, CRP, LBP) in plasma/serum
  - Kidney function markers (e.g., urine and serum creatinine, BUN/urea clearance, sodium, proteinuria, fractional excretion of sodium and urea, and urine output)
  - Serology (immunoglobulin G [IgG], IgE, and total immunoglobulin) in plasma/serum
  - Anti-drug antibodies in plasma/serum

- AP activity (pre-dose) in plasma/serum
- For patients who are ventilated:
  - Non-mechanical ventilation: non-rebreathing mask, or nasal oxygen delivery (liters of oxygen/min, estimated daily average)
  - Mechanical ventilation (non-invasive and invasive):
    - Arterial partial oxygen pressure (PaO2) (estimated daily average)
    - Fraction of inspired oxygen (FiO2) and positive end-expiratory pressure (PEEP) (estimated daily average)
    - Tidal volume (estimated daily average) for invasive mechanical ventilation only, and
    - To enable calculation of P/F ratio: PaO2 and FiO2 must be captured at the same time point. Only one simultaneous measurement will be used. In case of multiple measurements of this fraction the worst value must be used.
- Concomitant medication
- Recording start and stop date, name, and mean daily dose of vasopressor and inotropic therapy for determination of shock-free days
- Time from first diagnosis of SA-AKI to start of recAP treatment

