2.3. Other Objectives

To determine whether specific patient groups benefit most from recAP treatment and whether patient groups that are non-responders can be identified. The identification of such groups will be based on:

- Baseline characteristics, including:
 - Baseline kidney function marker (fractional excretion of sodium [FeNa], fractional excretion of urea [FE Urea])
 - Baseline tubular injury biomarkers (kidney injury molecule-1 [KIM-1], interleukin 18 [IL-18], alpha-glutathione s-transferase [GST-alpha])
 - Baseline biomarkers for systemic inflammation (IL-6, C-reactive protein [CRP], lipopolysaccharide-binding protein [LBP])
 - Baseline glomerular filtration rate (eGFR by chronic kidney disease epidemiology collaboration [CKD-EPI])
 - Baseline APACHE II score (<25, ≥25)
- Timing from first diagnosis of SA-AKI to start of recAP treatment, in time intervals (0 to < 6 hours, 6 to < 12 hours, 12 to < 18 hours, 18 to < 24 hours, ≥24 hours).
- Baseline Acute Kidney Injury Network (AKIN) stage (stage 1, stage 2, stage 3).

3. Investigational Plan

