Efficacy endpoints will be summarized for all four treatment groups excluding patients recruited whilst the interim analysis is performed to treatment arms not selected for Part 2. Any analyses of the other efficacy endpoints will compare the optimal recAP dose and placebo treatment groups only. All safety data will be summarized for all four treatment

groups including patients recruited at any point in the study. Similarly, all data listings will include patients recruited at any point in the study.

See also [Section 4.3](#) for definitions of the analysis sets used in the study, which also state which patients (i.e. recruited during Part 1, or recruited during Part 2) are included in each analysis set.

Display of data

Continuous variables will be summarized using descriptive statistics, including but not limited to the mean, standard deviation, median, lower quartile, upper quartile, minimum value, and maximum value. For the summary statistics of all numerical variables minimum and maximum will be displayed to the same level of precision as reported, unless otherwise specified. Mean, median, lower quartile and upper quartile will be displayed to one level of precision greater than the data collected. Standard deviation / standard error will be displayed to two levels of precision greater than the data collected. P-values will be rounded to three decimal places. If a p-value is less than 0.001 it will be reported as “<0.001.” If a p-value is greater than 0.999 it will be reported as “>0.999”.

Categorical variables will be summarized using frequency counts and percentages. When count data are presented, the percentage will be suppressed if the count is zero in order to draw attention to the non-zero counts. The denominator for all percentages will be the number of patients in that treatment within the analysis set of interest, unless otherwise specified. All percentages will be presented to one decimal place. Categorical summaries will display all categories available on the electronic case report form (eCRF). A row denoted “Missing” will be included in count tabulations only when information is missing for a categorical variable.

All data summaries will be provided by treatment arm.

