Please note that any patients who do not receive any dose of study drug will be excluded from the safety and PP analyses, and therefore do not need to be considered in the [Table 4-1](#). Dose windows were constructed in line with the weight ranges and corresponding pre-calculating volumes displayed in [Table 15-3](#). See [Section 15.3](#) for full justification of these windows.

Statistical Analysis

All statistical tests will be two-sided and performed using a 5% significance level, displaying 95% two-sided confidence intervals (CIs), unless specifically stated otherwise. As the primary efficacy endpoint is analyzed at the interim analysis and at the end of the study, multiplicity will be addressed by using a combination test to combine the results (see [Section 8.1.1](#)). A hierarchical method will be employed to address any multiplicity arising from the analysis of the key secondary endpoint. In other words, the formal analysis of this endpoint will be performed only if a statistically significant result is obtained from the combination test analysis of the primary endpoint. All analyses performed on the other secondary endpoints are for exploratory purposes only; therefore, no further multiplicity adjustment is required.

All analyses will be undertaken using SAS[®] Version 9.2 (SAS Institute, Inc, Cary, North Carolina) or later.

Weight

Body weight (in kg or lb) will be measured or estimated at screening. Weight will be displayed in kg and derived from lb as:

$$Weight[kg] = \frac{Weight[lb]}{2.2046}$$

Temperature

Temperature (in °C or °F) will be measured from Day 1 – Day 28. Temperature will be displayed in °C and derived from °F as:

$$Temperature[°C] = \frac{Temperature[°F] - 32}{1.8}$$

Laboratory Data

For laboratory data that are recorded as values of '<x' and '>x' where x is any numeric value, the numeric part after the '>' and '<' (i.e. x) will be used for summarizing and in graphical presentations. In addition the numeric part will be used in the derivation of the quartile-based subgroup definitions.

In the tables where serum creatinine or CRP data are presented, if a subject has missing baseline central laboratory measured serum creatinine or CRP values, but has available baseline local laboratory measured values then the local laboratory values will be used to

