7.2.1. Extent of Exposure

The number and percentages of patients that received any dose on Day 1, Day 2 and Day 3 will be summarized by treatment group. The number and percentages of patients will also be presented by total number of doses received (1 dose, 2 doses, 3 doses) by treatment group. All summaries will be performed using the Safety Set. The number and percentage of patients who discontinued the study prior to receiving treatment on Day 1, Day 2 and Day 3 will also be included.

Study Drug Infusion information will be presented in the form of a listing for the Safety Set, including: was patient dosed (Yes, No); infusion start time; infusion end time; route of

administration (central line, peripheral line); volume of all 4 vials drawn into the 50 mL syringe (yes, no); volume from the 4 vials discarded from the syringe based on patients weight (mL); saline added to the 50 mL syringe (mL), was total volume of 50 mL syringe administered (yes, no), and, if no, reason why total volume was not administered; and total volume of study drug administered (mL).

8. Efficacy Analysis

A hierarchical method will be employed to address any multiplicity arising from the analysis of the key secondary endpoint. In other words, the formal analysis of this endpoint will be performed only if a statistically significant result is obtained from the combination test analysis of the primary endpoint. All analyses performed on the other secondary endpoints are for exploratory purposes only; therefore, no further multiplicity adjustment is required. The results of this hierarchical method will be presented indicating where statistically significant results are obtained.

To provide an overall summary of the efficacy analyses, a table will be produced containing the results and magnitude of difference between the optimal recAP dose and placebo treatment groups for certain key endpoints. This table will be based on the ITT Combined Set.

Supportive analysis will be undertaken on a selection of endpoints (AUC_{1-7} and RRT incidence from Day 1 to Day 28, inclusive) including specific group categories as factors to assess the consistency of treatment effects.

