Results from the primary analysis for interim analysis at Part 1 and for Part 2 will include least square means for each treatment and the difference in least squares means between the treatment groups will also be presented along with the associated 95% CI. P-values will be presented for least square mean treatment differences. The one-sided p-value for the combined analysis will be presented with the sample sizes and one-sided p-values from the interim analysis at Part 1 and at Part 2.

Descriptive statistics for the primary endpoint and mean standardized endogenous creatinine clearance at Day 1 to Day 7 will also be presented in a summary table by

treatment. This will be presented for all four treatment groups for the ITT Combined, ITT part 1 Interim, PP Day 1-7 Part 1, and also for the optimal recAP dose and placebo treatment groups for the ITT Part 2 and PP Day 1-7 Part 2 Sets. Analysis on the PP Set will be used as a supplement to the ITT analysis. The ITT Part 1 Interim Set (for all four treatment groups) will also be produced to help check the assumption of the combined analysis that patients recruited in each part of the study belong to the same overall patient population.

The primary endpoint, AUC_{1-7} , and standardized endogenous creatinine clearance at Day 1 to Day 7 will be listed.

A time-course plot of standardized endogenous creatinine clearance with associated error bars on each day will be presented for the optimal recAP dose and placebo groups. This plot will be repeated three times using different selection criteria for the data based on data imputation and adjudication of creatinine clearance data:

- 1) Including only calculated values (i.e. no imputed values)
- 2) Including all (non-adjudicated) calculated and imputed values
- 3) Including only adjudicated calculated and imputed values

The combined ITT analysis primary endpoint summary and analysis will be repeated as a supportive sensitivity analysis, excluding patients who died before day 8, with SAS[®] output from Part 1 and Part 2 models included on the primary combined analysis output. Additionally, descriptive statistics for the primary endpoint and mean time-corrected endogenous creatinine clearance at Day 1 to Day 7 will be presented in a summary table for the ITT Combined Set by treatment group and subgroup category, defined in [Section 8.1.5](#).

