8.1.5. Supportive Analysis for the Primary Efficacy Endpoint

Due to the high variability of the creatinine clearance, the change from baseline in serum creatinine at Day 7 will be analyzed using an ANOVA with baseline serum creatinine, treatment (optimal recAP dose and placebo) and site as explanatory variables. The analysis will be run on the ITT Combined Set. If there is more than one serum creatinine result collected at Day 7, the average at Day 7 will be used to derive the change from baseline.

Additionally the primary endpoint analysis will be repeated with the following variables as additional factors within the ANOVA model for the ITT Combined Set (for the optimal recAP dose and placebo):

- Baseline biomarkers for kidney function:
 - Fractional excretion of sodium (<1%, ≥1 % - ≤2%, >2%).
 - Fractional excretion of urea (<35%, ≥35%).
- Baseline AKIN stage (stage 1, stage 2 and stage 3).
- Microbial infection. The following are the five possible outcomes:
 1. Gram positive
 2. Gram negative
 3. Mix gram positive/gram negative
 4. Other (e.g. fungal)
 5. Unknown.

If a blood culture is available this is leading. (Note that if a staphylococcus epidermis is the outcome this is a contamination and should be ignored). If no blood culture is available, the culture from the site for which the patient was hospitalized (index indication) is leading e.g. patient hospitalized for lung infection, with positive sputum and positive urine culture: sputum is then leading.

- Baseline urinary biomarkers for proximal tubular cell damage:

- KIM-1 (<Q1, ≥Q1 - <Q2, ≥Q2 - <Q3, ≥Q3).
- IL-18 (<Q1, ≥Q1 - <Q2, ≥Q2 - <Q3, ≥Q3).
- GST-alpha (<Q1, ≥Q1 - <Q2, ≥Q2 - <Q3, ≥Q3).

For GST-alpha, two different kits were used in the testing of GST-alpha therefore quartiles will be calculated separately for each kit and then for each subject, their baseline value will be compared against the quartile for the kit that was used to assess their GST-alpha baseline result. The resulting assigned quartile categories will then be combined together for subgroup summaries regardless of which kit was used.

- Baseline biomarkers for systemic inflammation:
 - IL-6 (<Q1, ≥Q1 - <Q2, ≥Q2 - <Q3, ≥Q3).
 - CRP (<Q1, ≥Q1 - <Q2, ≥Q2 - <Q3, ≥Q3).
 - LBP (<Q1, ≥Q1 - <Q2, ≥Q2 - <Q3, ≥Q3).
- Baseline eGFR by CKD-EPI formula (<Q1, ≥Q1 - <Q2, ≥Q2 - <Q3, ≥Q3).
- Time from first diagnosis of SA-AKI to start of recAP treatment (0 to <6 hours, 6 to <12 hours, 12 to <18 hours, 18 to <24 hours, ≥24 hours).

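### As written, the subgroup factor models for AUC1-7 and RRT specify no treatment-by-factor term, so they cannot show whether the treatment effect is consistent across subgroups

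*SAP*

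**What the plan says.** - **Purpose.** The opening of SAP Section 8 announces supportive analyses of AUC1-7 and RRT incidence "including specific group categories as factors to assess the consistency of treatment effects". SAP 2.3 gives the underlying objective: "To determine whether specific patient groups benefit most from recAP treatment and whether patient groups that are non-responders can be identified".
- **AUC1-7 model.** The base model in SAP 8.1.1 is an ANOVA with treatment and site. SAP 8.1.5 then says: "Additionally the primary endpoint analysis will be repeated with the following variables as additional factors within the ANOVA model for the ITT Combined Set". The comparison is between optimal dose and placebo. Thirteen variables follow. The text does not say whether they enter one at a time or together.
- **RRT model.** SAP 8.2.1 uses logistic regression with treatment and site, and refers to 8.1.5 for the factor analysis.
- **Change history.** The version 3.0 entry for 8.1.5 agrees with the current text: the variables enter the models as covariates and no longer define by-groups.
- **Descriptive tables.** SAP 8.1.1 plans descriptive statistics "presented in a summary table for the ITT Combined Set by treatment group and subgroup category", and 8.1.5 adds summaries by factor and a table of patient numbers by arm and category. Under SAP Section 4, continuous summaries give statistics "including but not limited to the mean, standard deviation, median, lower quartile, upper quartile, minimum value, and maximum value".
- **Missing baseline factors.** Section 4 has two provisions. A row for missing values "will be included in count tabulations only when information is missing for a categorical variable". Local values are used in tables "if a subject has missing baseline central laboratory measured serum creatinine or CRP values, but has available baseline local laboratory measured values". No rule is given for a missing factor in these models.
- **Protocol.** Protocol 7.6 leaves cut-offs and outputs for the subgroups to the SAP.

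**The concern.** Whether an effect is consistent across groups, and which groups respond, are questions about how the treatment effect varies by level. A model with treatment, site and the factor, and no product term, has one treatment parameter. That parameter averages over the levels, whatever lies underneath. This holds whether the factors enter singly or jointly.

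What is at stake is interpretation. A treatment coefficient that hardly moves after adjustment could be reported as evidence of consistency when the model had no means of detecting the opposite. In the logistic model the reverse misreading is also possible: adding a prognostic factor can shift the odds ratio through non-collapsibility alone, which is not evidence of inconsistency. The responder and non-responder objective would then rest on differences worked out afterwards from descriptive tables.

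**Working it through.** **Inputs.** From SAP 4.1: 30 + 85 = 115 per arm for optimal dose and placebo; SD 49 mL/min; placebo mean 60; effective response 69.5 (effect 9.5); strong response 79 (effect 19). Tests are two-sided at 5% (SAP Section 4). RRT rates are assumed, because the documents give none.

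**The plan's own figure.** SAP 4.1 states no figure for the factor models. Simulating the two-part design with these inputs gives power of 82.0%, 79.5% and 85.9% with the low dose at 60, 69.5 and 79, against the stated 79% to 86%. The inputs are therefore sound to build on.

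**Size of the factor set.** Two factors have 2 levels, two have 3, seven have 4 and two have 5. That is 13 factors and 2×1 + 2×2 + 7×3 + 2×4 = 35 parameters if entered jointly.

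**What the additive model returns.** With equal levels balanced across arms, the coefficient is the average of the level effects: (19 + 0)/2 = 9.5, (28.5 − 9.5)/2 = 9.5 and (38 + 0 + 0 + 0)/4 = 9.5. Each equals the uniform case. Simulation (4,000 trials per pattern, 115 per arm, site ignored):

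| True effects by level (mL/min) | Mean coefficient | SE | Share p < 0.05 |
|---|---|---|---|
| 9.5, 9.5 | 9.35 | 6.47 | 0.30 |
| 19, 0 | 9.33 | 6.50 | 0.30 |
| 28.5, −9.5 | 9.46 | 6.59 | 0.30 |
| 9.5 in all four quartiles | 9.54 | 6.50 | 0.31 |
| 38, 0, 0, 0 | 9.57 | 6.59 | 0.31 |

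A second set with larger effects, (19, 19), (38, 0) and (48, −10), gave additive estimates of 19.0, 19.2 and 19.2, with rejection rates of 84%, 83% and 82%. With an interaction term in the model, that term was significant in 4%, 84% and 99.5%.

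**RRT (assumed rates).** A fall from 35% to 25% everywhere gives OR (0.25/0.75)/(0.35/0.65) = 0.619. A fall from 35% to 15% in half, with no effect in the rest, gives a common OR of 0.615, although the level ORs are 0.33 and 1.00.

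**What the remedy can and cannot do** (site ignored unless stated).
- Overall SE = 49 × √(2/115) = 6.46.
- Within a half: 49 × √(2/57.5) = 9.14, so the 95% CI is ±17.9. Within a quartile: 49 × √(2/28.75) = 12.92, so ±25.3.
- Interaction SE = 49 × √(2/(115p) + 2/(115(1−p))), which is 12.92 at p = 0.5 and 14.92 at p = 0.25. Power for a 19 mL/min difference in effect is 31% and 25%; for 38 it is 84% and 72%.
- Quartiles with effects 19, 19, 0, 0 and a 3-df test: 20%.
- Fixed site effects with an assumed 50 to 100 sites, equal halves: about 25% to 21% for 19 mL/min.
- RRT at an assumed 20% to 40% incidence: the within-half SE of the log OR is 0.466 to 0.381, so the CI spans a factor of 2.5 to 2.1 each way.
- False positives, if tests are independent: 1 − 0.95^13 = 0.49 per endpoint and 1 − 0.95^26 = 0.74 over both.

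**The case against.** **Consistency may mean robustness of the overall effect to baseline adjustment**, which an additive model can show. This is the strongest point, but it does not settle the matter. SAP 8.1.4 already plans that check separately, with baseline serum creatinine and APACHE II as added covariates, and SAP 2.3 asks about responders. If robustness was meant, Section 8 should say so, and the 2.3 objective would then have only descriptive support.

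**The by-category tables already show heterogeneity.** This stands in part. An unadjusted AUC1-7 difference and its CI could be derived from means, SDs and the per-arm counts, which come from the table in 8.1.5. The same would hold for an RRT odds ratio if counts by level are shown. These are unplanned derivations without site adjustment, and no comparison of levels is planned.

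**Low power and false positives make descriptive summaries a defensible choice.** The figures are right. They argue for estimates with intervals and against reliance on p-values. They do not make the additive model informative about consistency.

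**Stronger readings that the documents do not support.**
- A reader might infer that the SAP rules out interactions. It does not say so. Main effects only is an inference from the absence of any named interaction, and the change history supports it.
- A reader might infer that baseline urine is optional for all five urine-based factors (FeNa, FE urea, KIM-1, IL-18, GST-alpha). The qualifier "only required when possible within the 24-hour time window from first AKI diagnosis to treatment" in Protocol 6.2.2 belongs to the timed 6-hour collection. Protocol Table 13-1 marks the biomarker, FeNa and FE urea rows at baseline without it.
- A reader might infer a threat to the confirmatory result. SAP 8.1.5 labels all subgroup analyses exploratory.

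**Conclusion.** The concern holds. The factor analyses in SAP 8.1.5 and 8.2.1 do not serve the purpose stated in Section 8, because as written each model estimates one common treatment effect. Uniform benefit, benefit confined to half the patients, and benefit in half with harm in the rest give the same expected coefficient (9.5 mL/min in the worked case). The same happens for RRT, with a common OR of about 0.62 in both assumed patterns.

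The conclusion about the models does not depend on the assumed rates. The numerical illustrations assume 115 per arm, SD 49, levels balanced across arms and, except where stated, no site effects. The power figures are optimistic, because site effects, unequal levels and missing baseline factors all reduce them.

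The analyses are exploratory and the primary and key secondary tests do not change. The point is worth correcting because the present text invites a claim of consistency that the analysis cannot support.

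**What to change.** For each factor separately, for AUC1-7 and for RRT incidence, fit treatment, factor, treatment-by-factor and site. Report the treatment difference (odds ratio for RRT) with 95% CI in each level and the interaction p-value, labelled exploratory. A forest plot per endpoint would be a convenient display. Fix the following before unblinding:

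- **Sparse levels, AUC1-7.** Merge by patients per arm, for example fewer than 10 in either arm. Use the adjacent level for ordered factors and pooled classes for microbial infection. The category of 24 hours or more since diagnosis is a likely candidate, given exclusion criterion 17.
- **Sparse levels, RRT.** Merge by events and non-events per arm, for example fewer than 3 of either. A patient count alone is not enough: with 10 per arm and an assumed 20% incidence, the chance that at least one arm has no event is 1 − (1 − 0.8^10)² = 0.20. Where the model is still not estimable, show counts and percentages only.
- **Missing factor.** Analyse patients with a value and report the number missing by arm.
- **Site.** Drop it where the model is unstable, as 8.2.1 already allows for RRT.

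The thresholds are illustrations; the documents give none. State that power is low and the tests are unadjusted, that the emphasis is on estimates and CIs, and that neither a non-significant interaction nor a stable adjusted main effect shows consistency.

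The cost is one to four extra parameters per model, a few short rules and some added output, with no new data. The downside is wide intervals (about ±18 mL/min in a half, ±25 in a quartile), a false-positive chance of about 49% per endpoint or 74% over both, and some RRT levels reportable only as counts.
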